## 11.0 INVESTIGATOR'S RESPONSIBILITIES

### 11.1 INVESTIGATOR RESPONSIBILITY/PERFORMANCE

The investigator will ensure that this study is conducted in accordance with all regulations governing the protection of human subjects.

The investigator will ensure that all work and services described in or

associated with this protocol will be conducted in accordance with the investigational plan, applicable regulations, and the highest standards of medical and clinical research practice.

## **11.2 CONFIDENTIALITY**

The investigator must ensure that each subject's anonymity will be maintained and each subject's identity will be protected from unauthorized parties. A number will be assigned to each subject upon study entry and the number and the subject's initials will be used to identify the subject for the duration of the study. The investigator will maintain all documents related to this study in strict confidence.

## **11.3 INFORMED CONSENT AND PERMISSION TO USE PROTECTED HEALTH INFORMATION**

It is the responsibility of the investigator to obtain written informed consent from each subject participating in this study after adequate explanation, in lay language, of the methods, objectives, anticipated benefits, and potential hazards of the study. The investigator must also explain that the subject is completely free to refuse to enter the study or to discontinue participation at any time (for any reason) and receive alternative conventional therapy as indicated. Prior to study participation, each subject will sign an IRB approved informed consent form and receive a copy of same (and information leaflet, if appropriate). For subjects not qualified or able to give legal consent, consent must be obtained from a parent, legal guardian, or custodian.

The investigator or designee **must** explain to the subject before enrollment into the study that for evaluation of study results, the subject's protected health information obtained during the study may be shared with the study sponsor, regulatory agencies, and the IRB. It is the investigator's (or designee's) responsibility to obtain permission to use protected health information per HIPAA from each subject, or if appropriate, the subjects' parent or legal guardian.

## **11.4 SOURCE DOCUMENTATION AND INVESTIGATOR FILES**

The investigator must maintain adequate and accurate records to fully document the conduct of the study and to ensure that study data can be subsequently verified. These documents should be classified into two separate categories: (1) investigator study file and (2) subject clinical source documents that corroborate data collected on the CRF's. Subject clinical source documents would include hospital/clinic patient records; physician's and nurse's notes; appointment book; original laboratory, ECG, EEG, radiology, pathology, and special assessment reports;

pharmacy dispensing records; subject diaries; signed informed consent forms; and consultant letters. When the CRF or any form is used as the source document, this must be clearly stated in the investigator study file.

Minimally, the following be documented in source documents:

- ▶ Medical history/physical condition and diagnosis of the subject before involvement in the study sufficient to verify protocol entry criteria
- ▶ Study number, assigned subject number, and verification that written informed consent was obtained (each recorded in dated and signed notes on the day of entry into the study)
- ▶ Progress notes for each subject visit
- ▶ Documentation of treatment
- ▶ Laboratory test results
- ▶ Adverse events (action taken and resolution)
- ▶ Condition and response of subject upon completion of or early termination from the study

## 11.5 RECORDING AND PROCESSING OF DATA

If using hard copies of CRF's, study center personnel will complete individual CRF's in black ink. All corrections to entered data will be made by drawing a single line through the information to be corrected without obscuring it. All corrections will be initialed, dated and explained, if necessary. **Do not use “white-out” or obscuring correction tape.** A CRF is required for every patient who received any amount of study treatment. The investigator will ensure that the CRF's are accurate, complete, legible and timely. Separate source records are required to support all CRF entries.

## 11.6 NON-PROTOCOL RESEARCH

No investigative procedures other than those described in this protocol will be undertaken on the enrolled subjects without the agreement of the IRB.

## **11.7 Ethics**

The investigator agrees to conduct the study in compliance with the protocol, current good clinical practices, and all applicable (local, FDA, ICH) regulatory guidelines and standard of ethics.

## **11.8 Essential documents for the conduct of a clinical trial**

Essential documents are those documents with individually and collectively permit evaluation of the conduct of a trial and the quality of the data produced. These documents serve to demonstrate the compliance of the investigator with the standards of Good Clinical Practice and with all applicable regulatory requirements.

The following documents should be on file:

CV's and license of all investigators  
IRB documentation/correspondance  
Documentation of IRB certification

## APPENDIX I (02-21-2013)

STUDY PARAMETER TABLE (See Section 5.0 for details)										
	SURGERY			PRIOR to RT	DURING RT	FOLLOW-UP AFTER TREATMENT			Long-term Follow-up	
Assessment	Pre-Op	Intra-Op	Post-Op	PRIOR to RT		From END of RT			From End of RT	
		Week 1-4		Week 1-7	Week 5-8	1 Mo ± 1 wk.	3 Mo ± 2 wks	6 Mo ± 2 wks	12 Mo ± 2 wks	Thereafter, Every 6 Mo (± 1 Mo) and in years 2-5 at the discretion of the Investigator
Informed Consent	X									
Biopsy	X									
Surgical Frozen Section Path		X								
Pathology	X		X							
History/Physical	X		X	X	X	X	X	X	X	
ECOG 0-2	X			X		X	X	X	X	
Mammogram	X									
Pregnancy test	X									
Labs per MD discretion	X									
Radiological tests per MD discretion	X	X								
Operative Report			X							
Photographs *				X		X	X	X	X	
NAC sparing mastectomy		X								
RT Treatment Plan					X					
Cosmesis				X		X	X	X	X	
AE Evaluation			X	X	X	X				

\* Photographs will be taken at the discretion of the PI and Sub-PI

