### Treatment plan (07-15-2011)

Week 1	NAC-sparing mastectomy with immediate reconstruction
Between weeks 5 to 8	Prophylactic NAC irradiation twice daily, minimum of 4 hours apart, for 5 days , preferable in consecutive working days
2 weeks after irradiation	Chemotherapy, if indicated, at the discretion of the treating physician

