## **3.0 PATIENT SELECTION**

### **3.1 Inclusion Criteria**

- 3.1.1** Patients must have histologically confirmed in-situ or invasive breast carcinoma.
- 3.1.2** Tis, T1, T2 invasive or non-invasive carcinoma of the breast; lesion less than 4 cm.
- 3.1.3** Unifocal, multifocal or multicentric breast cancers that can be removed by nipple sparing mastectomy with negative surgical margins.
- 3.1.4** No extensive intraductal component or patient with distant metastases.
- 3.1.5** Patients must be > 18 years of age.

- 3.1.6** No concomitant or history of nipple discharge or skin involvement.
- 3.1.7** No prior history of malignancy (less than 5 years prior to study entry), except non-melanomatous skin cancer.
- 3.1.8** No prior history of radiation to the chest.
- 3.1.9** No collagenous disease (systemic lupus erythematosis, scleroderma, dermatomyositis). No previous non-hormonal therapy including radiation or chemotherapy for current breast cancer.
- 3.1.10** No patients with Paget's disease of the nipple.
- 3.1.11** No patients with co-existing medical conditions with life expectancy < 2 years.
- 3.1.12** No pregnant or lactating women.
- 3.1.13** ECOG 0 - 2.
- 3.1.14** Signed study-specific informed consent form prior to the study entry.

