### **3.2 Exclusion Criteria (08-06-2013)**

- 3.2.1** Retroareolar breast cancer lesions within one cm. depth from the skin surface.
- 3.2.2** Concomitant or history of nipple discharge or skin involvement.
- 3.2.3** Patient with distant metastases.
- 3.2.4** Patient with extensive intraductal carcinoma.
- 3.2.5** Any previously irradiated ipsilateral breast cancer.
- 3.2.6** Patients with Paget's disease of the nipple.
- 3.2.7** Patients with collagenous diseases, as systemic lupus erythematosis, scleroderma or dermatomyositis.
- 3.2.8** Other malignancy, except non-melanomatous skin cancer, less than 5 years prior to participation in this study.
- 3.2.9** Patients who are pregnant or lactating due to potential exposure of the fetus to RT and unknown effects of RT to lactating females.
- 3.2.10** Positive surgical margins following nipple sparing mastectomy

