## 4.0 TREATMENT PLAN

Week 1	NAC-sparing mastectomy with immediate reconstruction
Between weeks 5 to 8	Prophylactic NAC irradiation twice daily, minimum of 4 hours apart, for 5 days , preferable in consecutive working days;
2 weeks after irradiation	Chemotherapy, if indicated, at the discretion of the treating physician

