### **5.4 Pathologic evaluation of specimens**

Pathologic examination of the frozen section of the tissue underneath the NAC will be performed at the time of surgical procedure and results will be recorded in the study records. If pathology is positive, the patient will be taken off the study as screen failure. If pathology is negative, the surgeon will then perform a Skin Sparing Mastectomy, sparing the NAC. If the patient's NAC tissue biopsy is negative by frozen, but positive after standard hematoxylin and eosin, the patient will be taken off the study and the discussion will be done with the patient about options of removal of the NAC or postoperative irradiation of NAC outside the protocol.

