## 10.0 STATISTICAL CONSIDERATIONS

### 10.1 Study Size

For the purpose of dose escalation of NAC-radiation treatment, **evaluable patients** will be defined as any eligible patient that begins NAC irradiation treatment. However to evaluate feasibility of the NAC-sparing mastectomy with reconstruction, any patient who undergo surgery will be considered evaluable.

Following the dose escalation/de-escalation procedure described in section 4.2, we anticipate that 12 to 18 evaluable patients will be enrolled in this phase I study *during the dose-finding part*. The **number of evaluable patients** that will be needed depends on the number of times the NAC-radiation dose is escalated or possibly de-escalated. If the escalation occurs from dose level II up to dose level IV, between 14-18 evaluable patients will be required. If the dose is de-escalated after dose level II been evaluated in 6 patients, then 12 evaluable patients will be required, assuming 6 patients would be evaluated at dose level I. With 6 evaluable patients, the probability of not escalating when the true DLT rate is 35% is 68%. If the true DLT rate is 20%, the probability that the dose will be escalated is 66%.

A maximum of 6 patients per year is expected to be enrolled, since each patient must be evaluated for a minimum of 35 days and at most two patients will be enrolled simultaneously (within < 30 days after completion of the 5 days NAC radiation treatment). Thus, the expected accrual period is between 2-3 years.

An **additional expansion cohort of 12 patients** will be enrolled at the “**potential**” **recommended phase II dose (RP2D)** over an expected accrual period of 2 years.

To gather data on recurrence and survival, all patients will be followed at their clinic visits as clinically indicated.

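### Pregnancy is excluded because of fetal exposure to radiation, yet the only scheduled pregnancy test is pre-operative, at least 22 days before the first fraction (calendar-week reading), and is not repeated

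*Combined protocol and SAP*

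**What the plan says.** Section 3.1.12 of the inclusion criteria reads "No pregnant or lactating women". Section 3.2.9 of the exclusion criteria repeats the bar and gives its reason: "Patients who are pregnant or lactating due to potential exposure of the fetus to RT and unknown effects of RT to lactating females".

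The Appendix I study parameter table has one row labelled "Pregnancy test", with a single mark in the Pre-Op column. No window before surgery is given. The PRIOR to RT column lists history and physical, ECOG status, photographs, cosmesis and adverse events. The DURING RT column lists history and physical, the RT plan and adverse events. Neither has a pregnancy test, and discretionary laboratory tests are also marked only Pre-Op.

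The treatment plan (Protocol Summary and section 4.0) places "NAC-sparing mastectomy with immediate reconstruction" in week 1 and gives the time of irradiation as "Between weeks 5 to 8", delivered over 5 days. Section 4.2 requires a planning CT but no pregnancy test, and section 5 adds none.

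**The concern.** The hazard named in 3.2.9 is radiation, so pregnancy status matters most when radiation starts. The schedule checks it by test only before surgery, weeks earlier. A patient who conceives after that test, or whose conception was too recent for it to detect, can reach the first fraction with no scheduled test able to reveal it. ECOG status, another entry criterion, is assessed again before RT; the criterion justified by RT itself is not retested.

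What is at stake is patient safety: the fetal exposure that 3.2.9 is meant to prevent.

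**Working it through.** The protocol states no figure for the interval from test to RT, so there is none to reproduce. The interval follows from the treatment-plan tables.

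**Inputs.** Surgery in week 1; RT in weeks 5 to 8; RT lasting 5 days (sections 4.0 and 4.2.1). The test is no later than surgery (Appendix I, Pre-Op). Calendar week w covers days 7(w − 1) + 1 to 7w, so week 1 is days 1–7, week 5 starts on day 29 and week 8 ends on day 56.

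**Age of the test at the first fraction, if it is done on the day of surgery:**

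- Shortest: surgery on day 7, first fraction on day 29: 29 − 7 = 22 days.
- Longest, with all five RT days on consecutive days inside week 8: the latest first fraction is day 56 − 4 = 52, so 52 − 1 = 51 days.
- Longest, if only the first fraction must fall in week 8: 56 − 1 = 55 days.

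A test done before the day of surgery lengthens each figure by an interval the protocol does not set.

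**Other readings of the weeks:**

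| Reading | Shortest (days) | Longest (days) |
|---|---|---|
| Calendar weeks, surgery in week 1 | 22 | 51 (or 55) |
| Day 1 is the day of surgery | 29 − 1 = 28 | 51 (or 55) |
| 5 to 8 completed weeks after surgery | 5 × 7 = 35 | 8 × 7 = 56 |
| Surgery anywhere in weeks 1–4, the Appendix I header taken literally | 29 − 28 = 1 | 51 (or 55) |

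The last reading conflicts with both treatment-plan tables, which put surgery in week 1; the header plausibly spans the post-operative period as well. On every reading, no scheduled test is tied to the start of RT.

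**Effect of a repeat test.** With a window of 7 days before the first fraction (an assumption), the age of the latest test falls by at least 22 − 7 = 15 days at the short end. At the long end it falls by 51 − 7 = 44 days, or 55 − 7 = 48 if the first fraction can be on day 56. These are calendar-week figures, before the test-to-surgery interval is added.

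**Why a mark alone would not do.** Appendix I labels the PRIOR to RT column weeks 1–7. A test on day 1 would satisfy a bare mark there and could still be 51 days old (or 55) at the first fraction.

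**Patients concerned.** Section 10.1 gives at most 18 evaluable patients in dose-finding and 12 in the expansion cohort: 18 + 12 = 30. Only women of childbearing potential among them are affected, and their number is not given.

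**The case against.** The strongest reply is that the risk is small and partly covered. The field is the nipple-areola complex, and section 1.3 describes the electrons as superficial. History and physical is repeated after surgery, before RT and during RT, and section 8.1.4 lets the physician end participation at any time in the patient's interest. Section 3.3 has eligibility reviewed before study entry, so a baseline-only test is consistent with how entry criteria are generally handled. The consent pages were not seen and may contain contraception or pregnancy-reporting instructions.

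Most of this stands, and it limits how serious the point is. It does not supply a test. A history or examination may reveal a known pregnancy but can miss an early one, and 8.1.4 can be used only once someone suspects it.

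A reader might go further and infer that the protocol would let a known pregnancy be irradiated. The documents do not support that. Some criteria are plainly judged after surgery: exclusion 3.2.10 is "Positive surgical margins following nipple sparing mastectomy", and under section 5.4 a patient whose nipple-areola tissue proves "positive after standard hematoxylin and eosin, the patient will be taken off the study". Section 10.1 says evaluable patients "will be defined as any eligible patient that begins NAC irradiation treatment". Together these allow a reading in which a pregnancy found before RT is still an exclusion. The gap is in detection, not clearly in action.

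A reader might also take 48 days as the least that a repeat test would gain. It is the most favourable end of the calendar-week range, before the test-to-surgery interval, and applies only if the first fraction can fall on day 56.

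**Conclusion.** The point holds as a patient-safety gap in the schedule. Followed exactly, the plan can start RT on a pregnancy test that is 22 to 51 days old (up to 55 if RT may run past week 8), plus the unset interval between test and surgery. This rests on calendar weeks with surgery in week 1; other readings move the figures but leave the absence of a repeat test unchanged.

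The probability of an undetected pregnancy is low. Its size cannot be stated, because neither the number of women of childbearing potential nor any fetal dose is given. A reader might infer a threat to the recommended dose, but none follows: no dose-limiting toxicity item in 4.2.6 and no escalation rule in 4.2.5 refers to pregnancy. The change is worth making because it is cheap and checks the protocol's own safeguard when exposure begins.

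**What to change.** In Appendix I, add a pregnancy test for women of childbearing potential to the PRIOR to RT column. Attach a footnote requiring a negative result within a short set window before the first fraction, and stating that RT is not started if the result is positive. Seven days is one possible window, offered as an assumption; the planning CT visit may be a convenient occasion.

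The cost is one schedule entry, one footnote and one routine test, of a kind the trial already uses, for each woman concerned: about 30 at most. Some patients may need an extra draw or visit if their pre-RT visit falls outside the window. A very recent conception could still be missed, so the repeat narrows the gap without closing it.

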## APPENDIX II:

### NATIONAL CANCER INSTITUTE (NCI) COMMON TOXICITY CRITERIA (CTC)

The NCI CTC can be viewed on-line at the following NCI web site:

<http://ctep.cancer.gov/reporting/ctc.html>

### APPENDIX III:

#### DATA AND SAFETY MONITORING PLAN

The Sylvester Comprehensive Cancer Center (SCCC) Data and Safety Monitoring Committee (DSMC) will monitor this clinical trial according to the Cancer Center's DSM Plan. In its oversight capacity, the DSMC bears responsibility for suspending or terminating this study.

DSMC oversight of the conduct of this trial includes ongoing review of accrual and adverse event data, and periodic review of response to treatment or other study endpoint. The guidelines appearing in Section **10.3.1 to 10.3.3** are offered for DSMC consideration in assessing surgery-related toxicities. In addition, the DSMC will review reports from all audits, site visits, or study reviews pertaining to this clinical trial and take appropriate action.

The SCCC DSM Plan to which this study is subject can be obtained by calling the CRS office at [contact].

**Appendix IV:****DATA SUBMISSION SCHEDULE**

FORM	TO BE COMPLETED
BASELINE	
Eligibility Checklist	
SCCC Protocol Enrollment Form	Prior to registration
Consent Forms Signed/dated	
On-study Form	Within 30 days of registration
DURING PROTOCOL THERAPY	
	Due every week for phase I studies, every cycle for phase II-IV studies
AFTER PROTOCOL THERAPY	
Off Treatment Form	Within 14 days of discontinuation/completion of protocol therapy
FOLLOW-UP SCHEDULE (for studies with long term follow-up)	
Follow-up Form	1 month, 3 month, 6 month, 1 year, then every 6 months (+/- 1 month) and in years 2-5, at the discretion of the Investigator.
Progression/Relapse	Within 4 weeks of knowledge of progression/relapse
Notice of Death Form	Within 4 weeks of knowledge of death
Subsequent Malignancy	Within 4 weeks of knowledge of another malignancy

**NOTE: FORMS WILL BE CONSIDERED PAST DUE 14 DAYS AFTER THE DUE DATE.**

## APPENDIX VI

### KARNOFSKY PERFORMANCE SCALE

- 100 Normal; no complaints; no evidence of disease
- 90 Able to carry on normal activity; minor signs or symptoms of disease
- 80 Normal activity with effort; some sign or symptoms of disease
- 70 Cares for self; unable to carry on normal activity or do active work
- 60 Requires occasional assistance, but is able to care for most personal needs
- 50 Requires considerable assistance and frequent medical care
- 40 Disabled; requires special care and assistance
- 30 Severely disabled; hospitalization is indicated, although death not imminent
- 20 Very sick; hospitalization necessary; active support treatment is necessary
- 10 Moribund; fatal processes progressing rapidly
- 0 Dead

### ZUBROD PERFORMANCE SCALE

- 0 Fully active, able to carry on all pre-disease activities without restriction (Karnofsky 90-100).
- 1 Restricted in physically strenuous activity but ambulatory and able to carry out work of a light or sedentary nature. For example, light housework, office work (Karnofsky 70-80).
- 2 Ambulatory and capable of all self-care but unable to carry out any work activities. Up and about more than 50% of waking hours (Karnofsky 50-60).
- 3 Capable of only limited self-care, confined to bed or chair 50% or more of waking hours (Karnofsky 30-40).
- 4 Completely disabled. Cannot carry on any self-care. Totally confined to bed or chair (Karnofsky 10-20).

**APPENDIX VII****AJCC STAGING SYSTEM BREAST, 6th Edition****DEFINITION OF TNM****Primary Tumor (T)**

Definitions for classifying the primary tumor (T) are the same for clinical and for pathologic classification. If the measurement is made by physical examination, the examiner will use the major headings (T1, T2, or T3). If other measurements, such as mammographic or pathologic measurements, are used, the subsets of T1 can be used. Tumors should be measured to the nearest 0.1 cm increment.

TX	Primary tumor cannot be assessed
T0	No evidence of primary tumor
Tis	Carcinoma in situ
Tis (DCIS)	Ductal carcinoma in situ
Tis (LCIS)	Lobular carcinoma in situ
Tis (Paget's)	Paget's disease of the nipple with no tumor

**Note:** Paget's disease associated with a tumor is classified according to the size of the tumor.

T1	Tumor 2 cm or less in greatest dimension
T1mic	Microinvasion 0.1 cm or less in greatest dimension
T1a	Tumor more than 0.1 but not more than 0.5 cm in greatest dimension
T1b	Tumor more than 0.5 cm but not more than 1 cm in greatest dimension
T1c	Tumor more than 1 cm but not more than 2 cm in greatest dimension
T2	Tumor more than 2 cm but not more than 5 cm in greatest dimension
T3	Tumor more than 5 cm in greatest dimension
T4	Tumor of any size with direct extension to (a) chest wall or (b) skin, only as described below.
T4a	Extension to chest wall, not including pectoralis muscle
T4b	Edema (including peau d' orange) or ulceration of the skin of the breast, or satellite skin nodules confined to the same breast
T4c	Both T4a and T4b
T4d	Inflammatory carcinoma

